8.2.1.1 Initial Tumor Imaging

Initial tumor imaging at Screening must be performed within 28 days prior to randomization. Tumor imaging performed as part of routine clinical management is acceptable for use as screening tumor imaging if it is of diagnostic quality and performed within 28 days prior to randomization. Expedited verification of absence of radiologic evidence of disease will be performed by BICR at Screening and will be used to determine participant's eligibility.

Tumor imaging at baseline includes the following:

- CT of the chest
- Triphasic CT (preferred) or MRI of the abdomen and pelvis

8.2.1.2 Tumor Imaging During the Study

The first on study imaging assessment should be performed at 12 weeks (± 7 days) from the date of randomization. Imaging should be performed Q12W until Week 228 (± 14 days) (~Year 4), Q24W thereafter until Week 260 (± 14 days) (~Year 5), and annually thereafter for up to 2 years (~Year 7) or until any initial recurrence (intrahepatic or extrahepatic), whichever occurs first. Follow the schedule below after initial recurrence based on intra-hepatic or extra-hepatic recurrence. Recurrence should be BICR-verified or confirmed with pathology if required per the site's standard of care.

- If BICR-verified intrahepatic recurrence with absence of extra-hepatic recurrence, tumor imaging should be performed Q24W thereafter until Week 260 (± 14 days) (~Year 5), and annually thereafter for up to 2 years (~Year 7), until extra-hepatic disease recurrence is documented radiographically by the investigator (with site radiologist) and verified by BICR. Disease recurrence can also be confirmed with pathology if required per the site's standard of care.
- Imaging should be discontinued after extra-hepatic recurrence that is verified by BICR. Disease recurrence can also be confirmed with pathology if required per the site's standard of care.

Imaging timing should follow calendar days from randomization and should not be adjusted for delays in cycle starts. Imaging should continue to be performed until extra-hepatic disease recurrence is identified by the Investigator and verified by BICR or confirmed with pathology if required per the site's standard of care, withdrawal of consent, death, or notification by the Sponsor, whichever occurs first.

8.2.1.3 End-of-Treatment and Follow-up Tumor Imaging

For participants who discontinue study intervention, tumor imaging should be performed at the time of treatment discontinuation (± 4 week window). If previous imaging was obtained within 4 weeks prior to the date of discontinuation, then imaging at treatment discontinuation is not mandatory.

For participants who DC study intervention for reasons other than BICR-verified disease recurrence or BICR-verified intra-hepatic recurrence, imaging should continue to be performed as if on study (see Sec. 8.2.1.2) until extra-hepatic disease recurrence is verified by BICR, pregnancy, death, withdrawal of consent, or the end of the study, whichever occurs first.

NOTE: Participants who do not have confirmed extrahepatic recurrence, but decline study-specific imaging in Efficacy Follow-Up and move to Survival-Follow Up Phase, should be encouraged to submit imaging performed as standard of care (even retrospectively) in the Survival-Follow Up Phase.

8.2.2 Patient-reported Outcomes

The EQ-5D-5L and EORTC QLQ-C30, and EORTC QLQ-HCC18 questionnaires will be administered by trained site personnel and completed by participants in the following order: EQ-5D-5L first, then EORTC QLQ-C30, then EORTC QLQ-HCC18. The questionnaires should be administered prior to dosing on Day 1 of each cycle from Cycle 1-10 both inclusive, then on Day 1 of Cycle 12, 14, 16, at EOT, and at the 30-day Safety Follow-up Visit. For participants who discontinue from study intervention prior to Cycle 17, PROs will be collected Q12W from the EOT Visit during the remainder of Year 1. After Year 1, PROs are to be performed Q24W to align with imaging visits. After Year 2, PROs are to be performed Q24W to align with imaging visits, up to and including Week 216. PROs are collected again at Week 228, and Week 252 PROs should be collected up to and including Year 5 (Week 252).

It is best practice and strongly recommended that patient-reported outcomes (PROs) are administered to randomized participants prior to drug administration, AE evaluation, and disease status notification. If the participant does not complete the PROs at a scheduled time point, the MISS_MODE form must be completed to capture the reason the assessment was not performed.

NOTE: For some sites, the translated EORTC QLQ-C30 and/or EORTC QLQ-HCC18 might become available after study startup and should be administered to participants at their time of enrollment; for some sites, the EORTC QLQ-C30 and/or EORTC QLQ-HCC18 translation might not be available for the entire duration of the study.

8.3 Safety Assessments

Details regarding specific safety procedures/assessments to be performed in this study are provided. The total amount of blood/tissue to be drawn/collected over the course of the study

(from Screening to End-of-Treatment), including approximate blood/tissue volumes drawn/collected by visit and by sample type per participant, can be found in the Laboratory Manual.

Planned time points for all safety assessments are provided in the SoA.

8.3.1 Physical Examinations

A complete physical examination will be conducted by an investigator or medically qualified designee (consistent with local requirements) as per institutional standard. Height will be measured at Screening only. Weight will be measured per Section 1.3.

A brief directed physical examination will be conducted by an investigator or medically qualified designee (consistent with local requirements) per institutional standard.

Investigators should pay special attention to clinical signs related to previous serious illnesses.

8.3.1.1 Full Physical Examination

The investigator or qualified designee will perform a complete physical examination during the Screening period within 7 days prior to C1D1. Clinically significant abnormal findings should be recorded as medical history. The time points for full physical exams are described in Section 1.3. After the first dose of study intervention, new clinically significant abnormal findings should be recorded as AEs.

Investigators should pay special attention to clinical signs related to previous serious illnesses, ascites, and evidence of encephalopathy.

8.3.1.2 Directed Physical Examination

For clinic visits that do not require a full physical examination as defined in Section 1.3, the investigator or qualified designee will perform a directed physical examination, as clinically indicated, prior to study intervention administration. New clinically significant abnormal findings should be recorded as AEs.

Investigators should pay special attention to clinical signs related to previous serious illnesses, ascites, and encephalopathy.

8.3.2 Vital Signs

Temperature, pulse rate, respiratory rate, and blood pressure will be assessed.

Blood pressure and pulse measurements will be assessed with a completely automated device. Manual techniques will be used only if an automated device is not available.

Blood pressure and pulse measurements should be preceded by at least 5 minutes of rest for the participant in a quiet setting without distractions.

8.3.3 Electrocardiograms

Single 12-lead electrocardiogram (ECG) will be obtained after participant has been recumbent for 5 minutes and reviewed by an investigator or medically qualified designee (consistent with local requirements) as outlined in the SoA (see Section 1.3) using an ECG machine that automatically calculates the heart rate and measures PR, QRS, QT, and QTc intervals.

An ECG abnormality may meet the criteria of an AE as described in this protocol (see Appendix 3) and the case report form (CRF) Completion Guidelines. In these instances, the AE corresponding to the ECG abnormality will be recorded on the appropriate CRF.

8.3.4 Child-Pugh Score

Originally developed in 1973, the Child-Pugh score was used to estimate the risk of operative mortality in participants with bleeding esophageal varices. It has since been modified, refined, and become a widely used tool to assess prognosis in patients with chronic liver disease and cirrhosis. The score considers 5 factors, 3 of which assess the synthetic function of the liver (ie, total bilirubin level, serum albumin, and coagulation parameters [INR or PT]) and 2 of which are based on clinical assessment (ie, degree of ascites and degree of hepatic encephalopathy; see Appendix 14). The investigator or qualified designee will determine the Child-Pugh score during the Screening period within 7 days prior to C1D1 and thereafter as outlined in the SoA.

8.3.5 Clinical Safety Laboratory Assessments

Refer to Appendix 2 for the list of clinical laboratory tests to be performed and to the SoA for the timing and frequency.

The investigator or medically qualified designee (consistent with local requirements) must review the laboratory report, document this review, and record any clinically relevant changes occurring during the study in the AE section of the case report form (CRF). The laboratory reports must be filed with the source documents. Clinically significant abnormal laboratory findings are those which are not associated with the underlying disease, unless judged by the investigator to be more severe than expected for the participant's condition.

All protocol-required laboratory assessments, as defined in Appendix 2, must be conducted in accordance with the Laboratory Manual and the SoA.

If laboratory values from nonprotocol-specified laboratory assessments performed at the institution's local laboratory require a change in study participant management or are considered clinically significant by the investigator (eg, SAE or AE or dose modification), then the results must be recorded in the appropriate CRF (eg, SLAB).

For any laboratory tests with values considered clinically significantly abnormal during participation in the study or within 30 days after the last dose of study intervention, every

attempt should be made to perform repeat assessments until the values return to normal or baseline or if a new baseline is established as determined by the investigator.

Details regarding specific laboratory procedures/assessments to be performed in this study are provided below. The total amount of blood/tissue to be drawn/collected over the course of the study (from Screening to End-of-Treatment visits), including approximate blood/tissue volumes drawn/collected by visit and by sample type per participant can be found in the Study Laboratory Manual. Refer to the SoA (Section 1.3) for the timing of laboratory assessments.

8.3.5.1 Laboratory Safety Evaluations (Hematology, Chemistry and Urinalysis)

Laboratory tests for hematology, chemistry, and urinalysis are specified in Appendix 2.

8.3.5.2 Pregnancy Test

All women who are being considered for participation in the study, and who are not surgically sterilized or postmenopausal, must be tested for pregnancy within 72 hours of the C1D1 and thereafter as outlined in the SoA. If a urine test is positive or not evaluable, a serum test will be required. Participants must be excluded/discontinued from the study intervention in the event of a positive test result. Refer to Appendix 7 for country-specific requirements.

8.3.6 Performance Assessments

8.3.6.1 Eastern Cooperative Oncology Group (ECOG) Performance Scale

The investigator or qualified designee will assess ECOG status (see Appendix 9) at screening within 7 days prior to C1D1, prior to the administration of each dose of study intervention, at EOT and during the follow-up period as specified in the SoA (Section 1.3).

8.4 Adverse Events (AEs), Serious Adverse Events (SAEs), and Other Reportable Safety Events

The definitions of an AE or SAE, as well as the method of recording, evaluating, and assessing causality of AE and SAE and the procedures for completing and transmitting AE, SAE, and other reportable safety event reports can be found in Appendix 3.

Adverse events, SAEs, and other reportable safety events will be reported by the participant (or, when appropriate, by a caregiver, surrogate, or the participant's legally authorized representative).

The investigator and any designees are responsible for detecting, documenting, and reporting events that meet the definition of an AE or SAE as well as other reportable safety events. Investigators remain responsible for following up AEs, SAEs, and other reportable safety events for outcome according to Section 8.4.3.

The investigator, who is a qualified physician, will assess events that meet the definition of an AE or SAE as well as other reportable safety events with respect to seriousness, intensity/toxicity and causality.

Adverse events will not be collected for participants during the prescreening period (for determination of archival tissue status) as long as that participant has not undergone any protocol-specified procedure or intervention. If the participant requires a blood draw, fresh tumor biopsy, etc., the participant is first required to provide consent to the main study, and AEs will be captured according to guidelines for standard AE reporting.

8.4.1 Time Period and Frequency for Collecting AE, SAE, and Other Reportable Safety Event Information

All AEs, SAEs, and other reportable safety events that occur after the participant provides documented informed consent, but before intervention allocation/randomization, must be reported by the investigator if the participant is receiving placebo run-in or other run-in treatment, if the event cause the participant to be excluded from the study, or is the result of a protocol-specified intervention, including, but not limited to washout or discontinuation of usual therapy, diet, or a procedure.

All AEs from the time of intervention allocation/randomization through 30 days following cessation of study intervention must be reported by the investigator.

All AEs meeting serious criteria, from the time of intervention allocation/randomization through 90 days following cessation of study intervention or 30 days following cessation of study intervention if the participant initiates new anticancer therapy, whichever is earlier, must be reported by the investigator.

All pregnancies and exposure during breastfeeding, from the time of intervention allocation/randomization through 120 days following cessation of study intervention, or 30 days following cessation of study intervention if the participant initiates new anticancer therapy must be reported by the investigator.

Additionally, any SAE brought to the attention of an investigator at any time outside of the time period specified above must be reported immediately to the Sponsor if the event is considered related to study intervention.

Investigators are not obligated to actively seek AEs or SAEs or other reportable safety events in former study participants. However, if the investigator learns of any SAE, including a death, at any time after a participant has been discharged from the study, and the investigator considers the event to be reasonably related to the study intervention or study participation, the investigator must promptly notify the Sponsor.

All initial and follow-up AEs, SAEs, and other reportable safety events will be recorded and reported to the Sponsor or designee within the time frames as indicated in [Table 6](#).

Table 6 Reporting Time Periods and Time Frames for Adverse Events and Other Reportable Safety Events

Type of Event	Reporting Time Period: Consent to Randomization/ Allocation	Reporting Time Period: Randomization/ Allocation through Protocol-specified Follow-up Period	Reporting Time Period: After the Protocol- specified Follow-up Period	Time Frame to Report Event and Follow-up Information to Sponsor:
Nonserious Adverse Event (NSAE)	Report if: - due to protocol-specified intervention - causes exclusion - participant is receiving placebo run-in or other run-in treatment	Report all	Not required	Per data entry guidelines
Serious Adverse Event (SAE) including Cancer and Overdose	Report if: - due to protocol-specified intervention - causes exclusion - participant is receiving placebo run-in or other run-in treatment	Report all	Report if: - drug/vaccine related. (Follow ongoing to outcome)	Within 24 hours of learning of event
Pregnancy/Lactation Exposure	Report if participant has been exposed to any protocol-specified intervention (eg, procedure, washout or run-in treatment including placebo run-in)	Report all	Previously reported – Follow to completion/termination; report outcome	Within 24 hours of learning of event
Event of Clinical Interest (require regulatory reporting)	Report if: - due to intervention - causes exclusion	Hepatic ECIs except those considered due to disease progression as judged by the investigator	Not required	Within 24 hours of learning of event
Event of Clinical Interest (do not require regulatory reporting)	Report if: - due to intervention - causes exclusion	Report - non-hepatic ECIs and those not requiring regulatory reporting	Not required	Within 5 calendar days of learning of event

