Scheduled Timing	-28 to -1				At time of DC	30 days post last dose	Q12W Year 1 from RAND	Q12W Year 2-3 from RAND	Q24W for Year 4-5 from RAND	Annually for Year 6-7 from RAND	~Q12W	Post-treatment Period: Refer to Sections 8.11.2.1, 8.11.2.2, and 8.11.2.3
Window (days):		+3	±3	±3		+7	±7	±14	±14	±14	±14	
Child-Pugh score	X											Within 7 days prior to C1D1. Thereafter, only if any of the hepatic ECI criteria are met, document the Child-Pugh score with each visit until the hepatic ECIs resolve.

Study Period	Screening Phase	Intervention Phase (Every 3 Weeks and End After 17 Cycles of treatment)			End-of-Treatment	Post-Treatment Visits						Notes
Treatment Cycle		1	2	3 and onwards (up to 17 cycles)	DC	Safety Follow-up ^a	Efficacy Follow-up Visits				Survival Follow-up	Procedures should occur predose on Day 1 of each cycle unless otherwise noted.
Scheduled Timing	-28 to -1				At time of DC	30 days post last dose	Q12W Year 1 from RAND	Q12W Year 2-3 from RAND	Q24W for Year 4-5 from RAND	Annually for Year 6-7 from RAND	~Q12W	Post-treatment Period: Refer to Sections 8.11.2.1, 8.11.2.2, and 8.11.2.3
Window (days):		+3	±3	±3		+7	±7	±14	±14	±14	±14	
AE/SAE Review	X	<----->										AEs: monitored up to 30 days after last dose. SAEs and pregnancy: monitored up to 90 and 120 days after last dose, respectively, or 30 days after last dose if participant starts a new anticancer therapy, whichever occurs first.

Study Period	Screening Phase	Intervention Phase (Every 3 Weeks and End After 17 Cycles of treatment)			End-of-Treatment	Post-Treatment Visits						Notes
Treatment Cycle		1	2	3 and onwards (up to 17 cycles)	DC	Safety Follow-up ^a	Efficacy Follow-up Visits				Survival Follow-up	Procedures should occur predose on Day 1 of each cycle unless otherwise noted.
Scheduled Timing	-28 to -1				At time of DC	30 days post last dose	Q12W Year 1 from RAND	Q12W Year 2-3 from RAND	Q24W for Year 4-5 from RAND	Annually for Year 6-7 from RAND	~Q12W	Post-treatment Period: Refer to Sections 8.11.2.1, 8.11.2.2, and 8.11.2.3
Window (days):		+3	±3	±3		+7	±7	±14	±14	±14	±14	
Laboratory Procedures (LOCAL laboratory)	Clinical laboratory assessments may be conducted anytime within 72 hours prior to the scheduled visit, unless otherwise specified. Procedures/assessments should be performed prior to administration of study intervention.											

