4 STUDY DESIGN

4.1 Overall Design

This is a randomized, placebo-controlled, parallel-group, multicenter, double-blind Phase 3 study of adjuvant pembrolizumab versus placebo in participants 18 years of age and older with complete radiological response after surgical resection or local ablation. Staging of participants with complete radiological response after surgical resection will be defined per American Joint Committee on Cancer (AJCC) 8th Edition (Appendix 10) with adaptations based on tumor characteristics as established by the pathology report.

Study population will include participants with complete radiological response after surgical resection (R0 resection) of HCC and intermediate, high, or very high risk of recurrence and participants with complete radiological response after local ablation of HCC and intermediate or high risk of recurrence.

The intermediate risk of recurrence population will be capped at approximately 20% of all participants enrolled in the study.

Participants may be listed for liver transplantation in the status NT (not transplantable) during the course of the study. The risks of solid organ transplant after treatment with PD-1 inhibitor therapy have not been extensively studied. The timeframe for safe or appropriate solid organ transplantation after the last dose of pembrolizumab is unknown. Therefore, it is recommended not to perform solid organ transplantation within at least 120 days (5 half-

lives) of stopping pembrolizumab. The risks and benefits of transplant should be discussed with the participant by the treating investigator.

The Asia population [not including Japan] may be up to approximately 60% of the total study population.

CCI

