6.6 Dose Modification (Escalation/Titration/Other)

6.6.1 Immune-Related Events and Dose Modification (Withhold, Treat, Discontinue)

Dose Modification and Toxicity Management for Non-hepatic Immune-related AEs Associated with Pembrolizumab

AEs associated with pembrolizumab exposure may represent an immune-related response. These irAEs may occur shortly after the first dose or several months after the last dose of pembrolizumab treatment and may affect more than one body system simultaneously. Therefore, early recognition and initiation of treatment is critical to reduce complications. Based on existing clinical study data, most irAEs were reversible and could be managed with interruptions of pembrolizumab, administration of corticosteroids and/or other supportive care. For suspected irAEs, ensure adequate evaluation to confirm etiology or exclude other causes. Additional procedures or tests such as bronchoscopy, endoscopy, skin biopsy may be included as part of the evaluation. Based on the severity of irAEs, withhold or permanently discontinue pembrolizumab and administer corticosteroids.

Dose Modification and Toxicity Management Guidelines for Non-hepatic irAEs associated with pembrolizumab monotherapy, coformulations, or IO combinations are provided in [Table 4](#).

Table 4 Dose Modification and Toxicity Management Guidelines for Non-hepatic Immune-related Adverse Events Associated with Pembrolizumab Monotherapy, Coformulations or IO Combinations

General instructions: 1. Severe and life-threatening irAEs should be treated with IV corticosteroids followed by oral steroids. Other immunosuppressive treatment should begin if the irAEs are not controlled by corticosteroids. 2. Pembrolizumab monotherapy, coformulations or IO combinations must be permanently discontinued if the irAE does not resolve or the corticosteroid dose is not ≤ 10 mg/day within 12 weeks of the last treatment. 3. The corticosteroid taper should begin when the irAE is \leq Grade 1 and continue at least 4 weeks. 4. If pembrolizumab monotherapy, coformulations or IO combinations have been withheld, treatment may resume after the irAE decreased to \leq Grade 1 after corticosteroid taper.				
irAEs	Toxicity Grade (CTCAEv4.0)	Action With Pembrolizumab Monotherapy, Coformulations or IO Combinations	Corticosteroid and/or Other Therapies	Monitoring and Follow-up

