9.6.2.2 Assessment of Safety Topics of Special Interest

AEs that are immune-mediated or potentially immune-mediated will be evaluated separately. These events have been characterized consistently throughout the pembrolizumab clinical development program. Point estimates and 95% CIs for between-group difference are not expected to add value to the safety evaluation, and hence only number and percentage of participants with such pembrolizumab AEOSI will be provided, as well as the number and percentage of participants with corticosteroids administration to treat an AEOSI. Summary statistics will be provided for the analysis of time from first dose to the onset of an AEOSI.

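### Nonserious immune-mediated AEs starting more than 30 days after the last dose are not collected, although the protocol says such events can begin months later, and the AEOSI and SAE analysis windows are not stated

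*Combined protocol and SAP*

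**What the plan says.** The collection windows are the same in the synopsis, the Schedule of Activities (Section 1.3) and Section 8.4.1.

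- **Nonserious AEs.** Section 8.4.1: "All AEs from the time of intervention allocation/randomization through 30 days following cessation of study intervention must be reported by the investigator". The SoA note repeats it: "AEs: monitored up to 30 days after last dose". Table 6 lifts the reporting requirement for nonserious AEs once the follow-up period has ended.
- **SAEs.** Collected through "90 days following cessation of study intervention or 30 days following cessation of study intervention if the participant initiates new anticancer therapy", whichever comes first. Outside that period, any SAE that comes to the investigator's notice "must be reported immediately to the Sponsor if the event is considered related to study intervention".
- **Events of clinical interest (ECIs).** Section 8.4.1 gives no window. Table 6 does not require either class of ECI to be reported after the follow-up period.
- **Timing of immune-related AEs.** Section 6.6.1: "These irAEs may occur shortly after the first dose or several months after the last dose of pembrolizumab treatment".
- **Analysis.** SAP Section 9.6.2.2 reports the number and percentage of participants with an AEOSI and the number given corticosteroids for one. It adds: "Summary statistics will be provided for the analysis of time from first dose to the onset of an AEOSI". Section 9.6.2 states no analysis window for AEOSI or SAEs.

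**The concern.** Treatment lasts at most 17 doses, about a year, in people with no detectable disease, and Section 2.3 calls the benefit-risk profile in this population unknown. Participants who complete treatment all enter the post-treatment period in which, by the protocol's own account, immune-related events can still begin.

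If the plan is followed exactly, a thyroid, skin or other immune-mediated event that starts after day 30 and is managed without meeting a seriousness criterion never reaches the database. It is then absent from the AEOSI percentage, the steroid count and the onset-time distribution. The onset summary is affected most directly, because it is cut off at the end in which late events would appear.

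**Working it through.** The plan gives no figure for late immune-related AEs, so there is none to reproduce. The check compares the sections and then runs an arithmetic illustration.

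**1. Nonserious events.** Collection ends at day 30 (Section 8.4.1, SoA, Table 6). Onset may come months later (Section 6.6.1). No other rule picks up a nonserious AE with later onset, unless it is an ECI. Section 8.4.3 follows reported events to outcome, but that helps only events that began inside the window.

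**2. Steroid use.** The SoA medication note and Sections 6.5 and 8.1.5.2 record concomitant medication after day 30 only for SAEs and ECIs. Steroids given for a late nonserious event that is neither are not recorded, so the steroid count in Section 9.6.2.2 is truncated in the same way.

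**3. Serious events.** Up to day 90 every SAE is collected regardless of causality, unless new therapy intervenes. Later, or after an earlier cut-off, an SAE is reportable only if it is judged related and comes to the investigator's attention. Section 8.4.1 waives any duty to search for events in former participants. The SAP does not say whether these later related SAEs enter the AEOSI or SAE tables.

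**4. ECIs.** Section 8.4.1 is silent and Table 6 asks for nothing after the follow-up period. The medication rules in item 2 nevertheless presuppose ECIs beyond day 30. These texts do not settle when ECI collection ends.

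**5. New-therapy clause.** The shorter SAE limit is "30 days following cessation of study intervention if the participant initiates new anticancer therapy, whichever is earlier". For a participant starting new therapy on day 75, the earlier of 90 and 30 is day 30. Read literally, days 31 to 74 (44 days) are closed after the fact. However, Table 6 requires SAEs to reach the sponsor within 24 hours of the investigator learning of them, so most on those days would already have been reported. If new therapy starts by day 30, running the cut-off from that start, with a day-30 floor, changes nothing. What remains exposed is SAEs learned of late, and SAEs removed by an analysis window programmed from the literal text.

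**6. Illustration of size (assumptions only).** Let s be the share of nonserious immune-related AEs that start after the last dose, and c the fraction of those captured. The share missed is s × (1 − c). Neither s nor the onset pattern is in the documents, so s is taken as 5% to 20% with three onset patterns. For the first pattern, Section 4.1 equates 120 days with 5 half-lives, so the half-life is 120/5 = 24 days. Drug remaining at day 30 is 2^(−30/24) = 42%, and at day 90 it is 2^(−90/24) = 7.4%.

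| Onset pattern | c at day 30 | Missed, s = 5% to 20% | c at day 90 | Missed, s = 5% to 20% |
|---|---|---|---|---|
| Follows drug level | 58% | 2.1% to 8.4% | 93% | 0.4% to 1.5% |
| Uniform over 120 days | 25% | 3.8% to 15% | 75% | 1.3% to 5% |
| Uniform over 180 days | 17% | 4.2% to 16.7% | 50% | 2.5% to 10% |

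The range is 2% to 17% missed with collection to day 30, and 0.4% to 10% with collection to day 90.

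**The case against.** The case for leaving the plan alone has real force.

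- The windows agree wherever they are stated, so this is a deliberate choice. Section 6.6.1 is advice to clinicians on vigilance and sets no collection rule. This stands, but the AEOSI summaries are still cut off inside a period in which the protocol expects events.
- A reader might infer that all late immune-related harm goes uncounted. The documents do not support that. Serious events considered related remain reportable without time limit, and new therapy does not cancel this.
- A reader might infer that the new-therapy clause discards SAEs on a large scale and hides harm from pembrolizumab. The 24-hour reporting rule makes the real loss small. If pembrolizumab reduces recurrence, the clause would shorten placebo windows more often, which lowers the placebo SAE percentage and makes pembrolizumab look worse.
- A reader might size the clause from the stated control RFS median of 33.8 months: 1 − exp(−12 × ln 2/33.8) = 21.8% by 12 months, against 15.8% at an assumed hazard ratio of 0.7. These are RFS events, deaths included. They do not count new-therapy starts between days 31 and 90 after the last dose, so they do not measure lost SAEs.
- A reader might say that 90 of 120 days, or 75%, go uncovered. That counts days, not events. Section 4.1 gives the 120 days for transplantation ("it is recommended not to perform solid organ transplantation within at least 120 days"), and the inclusion criteria use the same figure for contraception. Neither defines an AE risk period.
- AEOSI and overall SAE percentages are descriptive, with no between-group interval in Table 9, so no formal conclusion depends on them. This limits the consequence.

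**Conclusion.** The point holds in a limited form. Nonserious immune-mediated AEs with onset after day 30 are not collected, and the three AEOSI summaries in Section 9.6.2.2 are truncated as a result. The amount cannot be determined from the documents. The 2% to 17% range rests wholly on the assumed late-onset share and onset pattern, and shows only that the loss could be anything from negligible to noticeable.

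Three gaps in specification accompany it: how late related SAEs are tabulated, when ECI collection ends, and from which date the new-therapy cut-off runs. The last has little practical effect.

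The primary efficacy analyses are not affected. This is an inexpensive improvement to the safety data in a disease-free population, and it does not show that the trial would give a misleading overall safety picture.

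**What to change.** The changes concern data collection and analysis only.

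- **(a)** Reconcile Section 8.4.1, Table 6 and the SoA note with Section 6.6.1 by collecting AEOSI and hepatic ECIs of any seriousness through the 90-day limit already used for SAEs. Follow-up contacts already scheduled can be used. With on-schedule dosing, dose 17 falls at Week 48 (16 × 3 weeks) and the Week 60 imaging visit is 84 days later, with a ±14-day window. Events up to day 90 not covered then can be asked about at the next contact. State the ECI window explicitly.
- **(b)** Reword the SAE clause so that collection ends at 90 days or at the start of new anticancer therapy, whichever is earlier, but not before day 30.
- **(c)** State in Section 9.6.2 the analysis windows for AEOSI and SAEs and how later related SAEs are counted. Keep a 30-day tabulation for comparison with other studies.

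The cost is protocol wording, an eCRF window change, some extra AE entry and slightly higher AEOSI rates than under the 30-day window. No visit, test or staff is added. Two limits remain: events starting after day 90 are still uncollected if nonserious, and symptomless events may still be missed because scheduled thyroid tests end at the end-of-treatment visit.
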